7.7.2. Management of Other Toxicities

Unless otherwise specified in Section 7.7, toxicities will be managed according to the guidelines below.

- All clinically significant Grade 3 and 4 laboratory abnormalities should be repeated within 3 calendar days to confirm toxicity grade. Confirmation of toxicity grade is required prior to the next dose of investigational medicinal product for any Grade 3 and 4 laboratory abnormality that in the opinion of the investigator is clinically significant and may pose a risk to the participant's safety.
- Clinical events and clinically significant laboratory abnormalities will be graded according to the GSI Grading Scale for Severity of Adverse Events and Laboratory Abnormalities (refer to [Appendix 4](#)).

Any questions regarding toxicity management should be directed to the Gilead medical monitor.

7.7.2.1. Grades 1 and 2 Laboratory Abnormality or Clinical Event Management of Clinical and Laboratory Adverse Events

- Grade 1 or 2 laboratory abnormality or clinical event

Continue investigational medicinal product at the discretion of the investigator.

7.7.2.2. Grades 3 Laboratory Abnormality or Clinical Event

- For Grade 3 clinically significant laboratory abnormality or clinical event, investigational medicinal product may be continued if the event is considered to be unrelated to investigational medicinal product.
- For a Grade 3 clinical event, or clinically significant laboratory abnormality confirmed by repeat testing, that is considered to be related to investigational medicinal product, investigational medicinal product should be withheld until the toxicity returns to \leq Grade 2.
- If a laboratory abnormality recurs to \geq Grade 3 following rechallenge with investigational medicinal product and is considered related to investigational medicinal product, then investigational medicinal product should be permanently discontinued, and the participant managed according to local practice including switching to an effective alternative ARV regimen with consideration of the long duration of exposure of investigational medicinal products and the risk of resistance if viremic. Recurrence of laboratory abnormalities considered unrelated to investigational medicinal product may not require permanent discontinuation.

7.7.2.3. Grade 4 Laboratory Abnormality or Clinical Event

For a Grade 4 clinical event or clinically significant Grade 4 laboratory abnormality confirmed by repeat testing that is considered related to investigational medicinal product, investigational medicinal product should be permanently discontinued, and the participant managed according to local practice including switching to an effective alternative ARV regimen with consideration of the long duration of exposure of investigational medicinal products and the risk of resistance if viremic. The participant should be followed as clinically indicated until the laboratory abnormality returns to baseline or is otherwise explained, whichever occurs first. A clinically significant Grade 4 laboratory abnormality that is not confirmed by repeat testing should be managed according to the algorithm for the new toxicity grade.

Investigational medicinal product may be continued without dose interruption for a clinically nonsignificant Grade 3-4 laboratory abnormality (eg, CK elevation after strenuous exercise, or triglyceride elevation that is nonfasting or that can be medically managed) or a Grade 3-4 clinical event considered unrelated to investigational medicinal product.

7.8. Safety Assessment Committee

Per Gilead's signal management and unblinding process, an internal Safety Assessment Committee can be requested to review unblinded clinical study for safety reasons. Members of the Safety Assessment Committee are not directly involved in conduct of the study. The Safety Assessment Committee provides recommendations to relevant safety committees (per Gilead's signal management process) whether further actions are necessary to protect participants involved in the LEN development program.

8. STATISTICAL CONSIDERATIONS

8.1. Analysis Objectives and Endpoints

8.1.1. Analysis Objectives

Study endpoints will be assessed in the Primary Cohort excluding the optional Pilot Cohort. Exploratory analysis may be conducted for the optional Pilot Cohort as applicable.

The primary objective of this study is as follows:

- To evaluate the safety and tolerability of a combination of the bNAbs GS-5423 and GS-2872 in combination with the HIV capsid inhibitor LEN

The secondary objectives of this study are as follows:

- To evaluate efficacy of the study regimens determined by the proportion of participants maintaining virologic suppression (HIV-1 RNA < 50 copies/mL) at Week 26
- To evaluate the PK of GS-5423, GS-2872, and LEN
- To evaluate immunogenicity of GS-5423 and GS-2872
- To evaluate the emergence of resistance to the components of the study regimens

The exploratory objectives are as follows:

- To evaluate changes in HIV reservoir
- To evaluate changes in immune biomarkers

8.1.2. Primary Endpoint

The primary endpoint of this study is as follows:

- Incidence of treatment-emergent SAEs through Week 26

8.1.3. Secondary Endpoints

The secondary endpoints of this study are as follows:

- Proportion of participants with HIV-1 RNA < 50 copies/mL at Week 26 as defined by the FDA-defined snapshot algorithm
- Proportion of participants with HIV-1 RNA \geq 50 copies/mL at Week 26 as defined by the FDA-defined snapshot algorithm

- Proportion of participants with positive anti-GS-5423 or anti-GS-2872 antibodies at Week 26
- Change from baseline in CD4+ cell counts at Week 26
- Treatment-emergent resistance to study drugs through Week 26
- Incidence of treatment-emergent SAEs through Week 26, and treatment-emergent AEs through Week 26
- PK parameters for GS-5423, GS-2872, and LEN (and metabolites, if applicable) as appropriate: AUC_{0-t} , AUC_{last} , $t_{1/2}$, C_{max} , T_{max} , T_{last} , C_t through Week 52

8.1.4. Other Endpoints of Interest

Other endpoints of interest are as follows:

- Changes from baseline in HIV-1 reservoir in PBMC at postbaseline visits
- Changes from baseline in HIV-1 specific T-cell response, immune cell phenotyping and proliferation, gene expression, antibody profiling, and plasma soluble proteins levels (eg, cytokines, chemokines, etc).

8.2. Planned Analyses

8.2.1. Interim Analysis

Prior to the final analysis, interim analyses will be conducted. The results from these analyses may be submitted to scientific meetings and for publications and to regulatory agencies to seek guidance for the overall clinical development program.

8.2.1.1 Gilead Data Review Committee Analysis

The GDRC will review the progress, unblinded safety and efficacy data of this study while the study is ongoing. The GDRC will convene after all participants enrolled in the Primary Cohort have completed their Week 12 visit or prematurely discontinued from the study.

No formal stopping rules will be used by the GDRC for safety outcomes. Rather, a clinical assessment will be made to determine if the nature, frequency, and severity of AEs associated with a study regimen warrant the early termination of the study in the best interest of the participants. Based on safety and preliminary efficacy, the GDRC will determine whether the optional Pilot Cohort will be implemented.

In addition, the GDRC may review unblinded safety and efficacy data on an ad hoc basis when there is a need for safety or efficacy monitoring. Refer to the GDRC Charter for additional details.

8.2.2. Primary Analysis

The unblinded primary analysis will be conducted after all participants in the Primary Cohort have completed Week 26 visit or prematurely discontinued from the study.

8.2.3. Final Analysis

The final analysis will be performed after all participants have completed the study or prematurely discontinued from the study, outstanding data queries have been resolved or adjudicated as unresolvable, and the data have been cleaned and finalized. The final analysis will include data from the Primary Cohort and may include data from the optional Pilot Cohort.

8.3. Analysis Conventions

8.3.1. Analysis Sets

8.3.1.1. All Randomized

The primary analysis set for by-participant listings is defined as the All Randomized Analysis Set, which will include all participants who are randomized into the study.

8.3.1.2. Efficacy

The primary analysis set for efficacy analysis is defined as the Full Analysis Set, which will include all randomized participants who have received at least one dose of the complete long acting study drug regimen (ie, SC LEN + GS-5423 and GS-2872).

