3.3. Study Treatments

This study will enroll approximately 20 participants (Primary Cohort). After GDRC review (Section 5.1.3), an optional Pilot Cohort of up to 20 additional participants may be added.

Participants in the Primary Cohort and in the optional Pilot Cohort will be randomized in a 1:1 ratio to one of the following 2 treatment groups based on the dose of GS-2872 as follows:

Treatment Group 1:

Oral LEN for loading 600 mg followed by LEN 927 mg SC on Day 1; oral LEN for loading 600 mg on Day 2

GS-5423 30 mg/kg, administered via IV infusion over 60 minutes on Day 1 (after LEN SC injection)

GS-2872 10 mg/kg, administered via IV infusion over 60 minutes on Day 1 (after GS-5423 infusion)

Treatment Group 2:

Oral LEN for loading 600 mg followed by LEN 927 mg SC on Day 1; oral LEN for loading 600 mg on Day 2

GS-5423 30 mg/kg, administered via IV infusion over 60 minutes on Day 1 (after LEN SC injection)

GS-2872 30 mg/kg, administered via IV infusion over 60 minutes on Day 1 (after GS-5423 infusion)

There is no stratification for randomization for the Primary Cohort.

For the optional Pilot Cohort, randomization will be stratified by the antibody (GS-5423 or GS-2872) to which the participant is sensitive.

All participants will discontinue their background oral ARV regimen 1 day prior to receiving study drugs on Day 1.

At Week 26, all participants will resume their baseline regimen of once daily oral ART (or compatible regimen selected by the investigator) and return to the clinic for visits at Weeks 38 and 52.

Unblinded treatment assignments will be provided to the investigators after all participants are back on their baseline ARVs (or compatible regimen selected by the investigator) at Week 26 or have discontinued the study, and the Week 26 analysis has been completed.

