5.3. Dosage and Administration of GS-5423, GS-2872, and Lenacapavir

On Day 1, all participants will receive the following study regimen:

- Oral LEN 600 mg will be administered orally (PO) with approximately 240 mL water, without regard to food.
- LEN 927 mg SC will be administered within 30 minutes after oral LEN for loading, as 2 SC injections at separate injection sites in the abdomen, within 15 minutes.
- GS-5423 30 mg/kg IV infusion will be administered immediately following (up to 1 hour after) the last SC LEN injection.
- GS-2872 10 mg/kg or 30 mg/kg (depending upon treatment group assignment) IV infusion will be administered at least 15 minutes following, and up to 1 hour after, the completion of GS-5423 IV infusion per [Table 5-1](#).

On Day 1, all study drugs should be administered on the same day (ie, no visit window is permitted for Day 1 study drug administration).

On Day 2, all participants will self-administer oral LEN for loading 600 mg with approximately 240 mL water, without regard to food, at approximately the same time as the oral LEN dose for loading on Day 1.

Dose and administration of LEN, GS-5423, and GS-2872 for Treatment Groups 1 and 2 are described below.

Table 5-1. Treatment Table

Study Day	Treatment Group 1	Treatment Group 2
Day 1	LEN 600 mg (two 300 mg tablets, PO) LEN 927 mg (two 1.5 mL injections, SC) GS-5423 30 mg/kg (IV infusion) GS-2872 10 mg/kg (IV infusion)	LEN 600 mg (two 300 mg tablets, PO) LEN 927 mg (two 1.5 mL injections, SC) GS-5423 30 mg/kg (IV infusion) GS-2872 30 mg/kg (IV infusion)
Day 2	LEN 600 mg (two 300 mg tablets, PO)	LEN 600 mg (two 300 mg tablets, PO)

IV = intravenous; LEN = lenacapavir; PO = per oral; SC = subcutaneous

Supportive medications, including but not limited to diphenhydramine, acetaminophen, and steroids, will be available in the clinic settings during the IV infusions.

Study drug infusion will be temporarily stopped if an infusion-related adverse reaction occurs. Symptom severity will be evaluated, and supportive medications provided as clinically indicated. Study drug infusion may be slowed and resumed after symptoms have resolved if approved by the investigator. If the symptoms, in the judgment of the investigator, compromise the ability to continue study-specific procedures and are considered to not be in the participant's best interests, or recurrent symptoms prevent completion of infusion, the infusion will be permanently discontinued.

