8.3.1.3. Safety

The primary analysis set for safety analyses is defined as the Safety Analysis Set, which will include all randomized participants who have received at least one dose of study drug.

All data collected during study will be included in the safety summaries.

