Whole Study Period Analysis includes efficacy (ie, HIV-1 RNA and CD4 cell count and percentage) and safety data collected during **Whole Study Period** from participants randomized and received at least one dose of study drug up to the end of the study (eg, Week 52). For efficacy summary, all HIV-1 RNA and CD4 data during the whole study will be included. For safety summary, all safety data collected up to the last exposure date (defined in Section 3.8.1) from participants who prematurely discontinued study or completed study will be included.

Data included in this analysis will be used to assess the efficacy and safety data collected during the study. Results will be summarized by treatment group and overall.

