3.1.2. Full Analysis Set

The Full Analysis Set (FAS) includes all randomized participants who have received at least one dose of the complete long acting study drug regimen (ie, SC LEN + GS-5423 and GS-2872), and do not have major protocol violation (defined as meeting exclusion criterion of having chronic hepatitis B virus (HBV) infection). This is the primary analysis set for efficacy analyses.

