6.2.2. Analysis of Other Efficacy Endpoints

6.2.2.1. Analysis of Proportion of Participants with HIV-1 RNA < 50 copies/mL by Missing = Failure and Missing = Excluded Approaches

Number and percentage of participants with HIV-1 RNA < 50 copies/mL by visit will be analyzed using the following 2 methods for imputing missing HIV-1 RNA values.

- Missing = Failure (M = F):
In this approach, missing data will be treated as virologic failure and summarized into the “missing” category (see list of HIV-RNA categories below).
- Missing = Excluded (M = E):
In this approach, missing data will be excluded in the computation of the percentages (ie, missing data points will be excluded from both the numerator and denominator in the computation). The denominator for percentages at a visit is the number of participants in the FAS with nonmissing HIV-1 RNA value at that visit.

For both M = F and M = E analyses, the number and percentage of participants with HIV-1 RNA in the following categories will be summarized by treatment group and total for Week 26 and other visits up to Week 26 for the LA Regimen Period Analysis, and up to Week 52 for the Whole Study Period Analysis based on the FAS:

- < 50 copies/mL
 - < 20 copies/mL
 - < 20 copies/mL Not Detectable
 - < 20 copies/mL Detectable
 - 20 to < 50 copies/mL
- 50 to < 200 copies/mL
- 200 to < 400 copies/mL
- 400 to < 1000 copies/mL
- ≥ 1000 copies/mL
- Missing (only applicable to M = F analysis)

The proportion of participants with HIV-1 RNA < 50 copies/mL as defined by the 2 different missing data imputation methods will be analyzed using the same statistical method applied to the secondary efficacy endpoint.

For the M = F analysis, the proportion of participants with HIV-1 RNA < 50 copies/mL will be plotted by treatment group for all visits up to Week 26 for the LA Regimen Period Analysis, and up to Week 52 for the Whole Study Period Analysis using the FAS.

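### The efficacy set requires all three long-acting drugs, so a participant who stopped ART and was dosed but missed one is in no suppression analysis, and the Week 26 rate can be overstated

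*Protocol*

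**What the plan says.** - **Efficacy set.** Protocol 8.3.1.2 defines the FAS as "all randomized participants who have received at least one dose of the complete long acting study drug regimen", naming SC LEN, GS-5423 and GS-2872. SAP 3.1.2 says the FAS "includes all randomized participants who have received at least one dose of the complete long acting study drug regimen" and adds that its members "do not have major protocol violation (defined as meeting exclusion criterion of having chronic hepatitis B virus (HBV) infection"). SAP 6.3 discloses that addition.
- **Safety set.** Protocol 8.3.1.3 is wider: "all randomized participants who have received at least one dose of study drug".
- **ART interruption.** Protocol 3.3: "All participants will discontinue their background oral ARV regimen 1 day prior to receiving study drugs on Day 1". Protocol 5.3 then gives oral LEN, SC LEN, GS-5423 and GS-2872 in that order on Day 1.
- **Stopped infusions.** Protocol 5.3 foresees that if "recurrent symptoms prevent completion of infusion, the infusion will be permanently discontinued".
- **Which set each suppression analysis uses.** The Week 26 snapshot uses the FAS (Protocol 8.5) and the Per Protocol set (SAP 6.1.3), and the latter is drawn from within the FAS (SAP 3.1.3). The Missing = Failure (M=F) and Missing = Excluded (M=E) tables use the FAS (SAP 6.2.2.1).
- **Whole Study efficacy.** SAP section 3 describes it as HIV-1 RNA and CD4 data "from participants randomized and received at least one dose of study drug up to the end of the study (eg, Week 52"). SAP 6.2.2.1 runs it "up to Week 52 for the Whole Study Period Analysis based on the FAS".
- **On-treatment window.** SAP 6.1.2 and Appendix 2 end on-treatment HIV-1 RNA at the earlier of ART restart and 196 days after the date on which all three long-acting drugs were given.

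**The concern.** Membership of the FAS is settled after randomization, after ART has been stopped and after the first dose. A participant who takes oral LEN, and perhaps SC LEN and GS-5423, but does not receive the last component has begun the strategy and carries its virologic risk. That person counts for safety in the Whole Study analysis but is missing from every suppression table. Because the Per Protocol set sits inside the FAS, it cannot show what the exclusion does.

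The secondary objective is the proportion who stay suppressed on the study regimens. If those who fall out would mostly count as non-successes, the reported rate describes people who got through all of Day 1 rather than all who left ART for the regimen. At about 20 participants, one person is about five percentage points. GS-2872 is given last and its dose is the only difference between the groups, so exclusions could also fall unevenly and affect the between-group comparison.

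Separately, SAP section 3 and SAP 6.2.2.1 name different populations for the same Whole Study analysis. A programmer cannot follow both.

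**Working it through.** **Inputs from the documents.** Primary Cohort of 20, true response 95%, bound 83% (95% less a 12-point margin), one-sided exact test at 0.025, power of at least 35% (Protocol 8.10, SAP 1.3). Allocation is 1:1, so about 10 per group (Protocol 3.3). Participants who discontinue are not replaced (Protocol 4.1.1).

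**Assumption.** The number dosed without the complete regimen, k, is not given, so a range is shown.

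**1. The plan's own figure.** When all n respond, the Clopper-Pearson 95% lower bound is 0.025^(1/n). For n = 20 it is 83.2%; for 19/20 it is 75.1%. Only 20/20 clears 83%. Power is 0.95^20 = 35.8%, and the exact one-sided error is 0.83^20 = 0.0241. The stated 35% reproduces.

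**2. How an excluded participant would score.** Under SAP 6.1.2 the Week 26 window opens on Study Day 176. Someone who restarts ART before then has no on-treatment result in the window. They fall in the category for 50 copies/mL or more, or in the no-virologic-data category; neither counts as below 50. Someone who stays off ART and is below 50 in the window would count as a success, provided an on-treatment cut-off is defined for them.

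**3. Effect on the rate with 20 dosed.** Let f completers fail and s of the k excluded participants be suppressed. The FAS rate is (20 − k − f)/(20 − k). The all-dosed rate is (20 − k − f + s)/20.

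With f = 0 and s = 0:

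| k | FAS rate (lower bound) | All-dosed rate (lower bound) | Difference |
|---|---|---|---|
| 0 | 20/20 = 100% (83.2%) | 20/20 = 100% (83.2%) | 0 |
| 1 | 19/19 = 100% (82.4%) | 19/20 = 95% (75.1%) | 5 points |
| 2 | 18/18 = 100% (81.5%) | 18/20 = 90% (68.3%) | 10 points |

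With one failure among completers (k = 1, f = 1, s = 0): 18/19 = 94.7% against 18/20 = 90.0%, or 4.7 points. In one group of 10 with k = 1: 9/9 = 100% against 9/10 = 90%.

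**4. The other direction.** With k = 1, f = 1 and s = 1, the FAS gives 18/19 = 94.7% and all dosed gives 19/20 = 95.0%, so the FAS is slightly low. If f = 0 and all k are suppressed, both rates are 100%.

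**5. The 83% bound.** With exactly 20 dosed and one excluded, the FAS lower bound (82.4%) and the all-dosed bound (75.1%) both miss 83%, so exclusion cannot turn a miss into a pass. If 21 are dosed and one non-success is excluded, the FAS gives 20/20 (83.2%, above 83%) against 20/21 = 95.2% (76.2%, below).

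**The case against.** A reader might infer four stronger things, and the documents do not support them.

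- **That the rate is overstated.** This needs at least one participant who missed a component and would not have counted as below 50 copies/mL. No such number is given, main dosing is supervised in a single visit, and steps 3 and 4 show cases with no bias and with a small reversal.
- **That any stopped infusion removes a participant.** Protocol 5.3 stops the infusion; it does not say that the next antibody is then withheld. SAP 3.1.3 lists partial or missed doses as a reason to leave the Per Protocol set from within the FAS, which suggests that partly dosed participants can be FAS members. Neither document says what counts as one dose of an infusion.
- **That intolerance is the cause.** SAP 3.8.1 has a rule for participants who took only oral LEN, and SAP 4.1 has one for non-completion because of a clinical hold. The latter is administrative.
- **That a planned success criterion is at risk.** The 83% bound appears only in the sample-size rationale. Protocol 8.5 and SAP 6.1.3 contain no test against it.

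The case for the current FAS also has weight. A complete-regimen set is a reasonable primary choice in a proof-of-concept study, and SAP 2.2 says the unblinded primary analysis has already been done, which is a poor time to redefine it. The primary endpoint, serious adverse events, has a whole-study safety set that includes everyone dosed. Exclusions will be visible through counts and reasons (SAP 3.1) and receipt of each drug (SAP 4.2.2). The section 3 mismatch does not reach the snapshot, because SAP section 6 exempts snapshot endpoints from the two-period scheme.

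Two points remain. Counts and reasons for exclusion do not give the suppression rate among all dosed participants. And the two SAP statements on the Whole Study population still disagree.

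**Conclusion.** The point holds as a gap in the supportive analyses and an inconsistency in the SAP, not as a demonstrated bias. With 20 dosed and all completers suppressed, each excluded participant who would have been a non-success raises the reported Week 26 rate by 5 points overall (10 in a group of 10). The effect is zero if nobody is in that position, and slightly negative if the excluded participant stayed suppressed while a completer failed. Overstatement is the likelier direction, because an early ART restart rules out a snapshot success, but it is not certain. The comparison with 83% could change only if more than 20 are dosed, which an enrolment of approximately 20 permits. All of this rests on an assumed k. The conflict between SAP section 3 and 6.2.2.1 needs correcting whatever k is.

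**What to change.** 1. Keep the FAS as the primary efficacy set.
2. Add a supportive Week 26 snapshot table, with exact confidence intervals by group and overall, on the Safety Analysis Set. Where no complete-regimen date exists, start the 196-day on-treatment limit from the first dose of study drug; the present anchor is undefined for these participants.
3. Run the Whole Study M=F and M=E tables on the any-dose population, as SAP section 3 states, so that section 3 and 6.2.2.1 agree.
4. State in SAP 3.1.2 whether a partial infusion counts as a dose for FAS membership.

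**Cost.** SAP wording and one more set of tables. No new collection is needed, since HIV-1 RNA is already scheduled at study, early termination and in-clinic post-termination visits. The supportive rate may be less favourable and will include participants who got only part of the regimen. Some may lack Week 26 data: Protocol 6.5 asks them to keep attending but allows shorter follow-up, partly by phone, or withdrawal. Because the primary analysis is already unblinded, the table should be labelled as added afterwards.
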